7.2 General Methodology

The DIAMOND-AF II Study is a prospective, non-randomized (single-group assignment) trial being performed at multiple centers in the United States, Canada and Europe.

If applicable, the following general comments pertain to the statistical analyses and data presentations:

- All statistical analyses will be performed using a one-sided hypothesis test at the overall 2.5% level of significance. P-values will be rounded to three decimal places. If a p-value is less than 0.001 it will be reported as "< 0.001." If a p-value is greater than 0.999 it will be reported as "> 0.999." No adjustments for multiplicity are planned.
- Continuous data will be summarized using descriptive statistics: number of subjects, mean, standard deviation or standard error, median, minimum and maximum. The decision to use either standard deviation or standard error will be based upon the objective of the presentation: standard deviation will be used when the interest is the natural variability of the data; standard error will be used when comparing two or more means. Continuous variables that are recorded using approximate values (e.g., < or >) will be replaced by the closest exact value for the calculation of summary statistics.
- Nominal categorical variables will be summarized using frequency counts and percentages.
- Ordinal variables may be analyzed as if they were continuously scaled and a combination of the above may be employed as appropriate: frequency and percentage of observations within a category and means and standard deviations of the scores of the categories.
- For categorical and ordinal variables, percentages will be calculated based on non-missing data.
- Baseline is defined as the last measurement for the outcome of interest obtained before the exposure to the study device.
- Duration variables will be calculated using the general formula: (end date start date)

Revision 1 Page 7 of 18

- All tables and listings will have a header showing the Sponsor name ("Medtronic"), the protocol number and the page number with the total number of pages in the listing or table. A footer will show the data extraction date, the file name, path, the program run date, along with notes and definitions for abbreviations used in the tables and listings.
- Within-subject changes will be calculated as visit value minus baseline value such that a negative change reflects a decrease and a positive change signifies an increase. The paired sample t-test or Wilcoxon Signed Rank test may be used to test if the mean (or median) within-subject change is equal to zero.
- MedDRA Version 20.0 or higher will be used for coding of all adverse events; WHO-Drug may be used for coding concomitant medications.
- Version 9.2 or higher of SAS® statistical software package or other validated statistical software will be used to provide all summaries, listings, graphs, and statistical analyses.

7.3 Center Pooling

Study analysis will use pooled data from all contributing study sites and geographies.

To evaluate homogeneity of treatment effect (safety and effectiveness primary endpoints) across geographies, the log-rank test will be used to compare results across the two geographical regions: US/Canada and Europe.

7.4 Handling of Missing, Unused, and Spurious Data and Dropouts

All available data will be used in data listings and tabulations.

Missing data due to early dropout on the primary endpoints may occur if a subject receives study treatment but discontinues prematurely from the study without experiencing a primary safety or effectiveness failure event.

The main analysis of the primary objectives will use available data with no imputations for missing data, where subjects who discontinue prematurely will be censored at their last study contact date in the Kaplan-Meier analysis.

Additionally, to assess the potential impact of missing data due to early dropout on the primary objectives, a tipping point analysis will be performed where subjects who discontinue prematurely will be iteratively imputed as failures in the order of their censoring times. The tipping point is defined as the number of imputed failures when the one-sided 97.5% confidence bound of the endpoint estimate crosses the performance goal (11.5% for primary safety and 40% for primary effectiveness).

Analysis of the secondary and ancillary objectives and any other study data will use available data with no imputations for missing data.

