10.7.7 Alternative Methods for Follow-Up Visits

Alternative methods of data collection may be necessary in the case of extenuating circumstances, such as a global pandemic, when subjects are prohibited from coming into the office for required assessments. These are listed below as “alternative processes used only during extenuating circumstances”. Data unable to be collected remotely or via an alternative method should be collected at the next possible in-person visit.

In the event a subject is unable to return for an in-office follow-up visit, the alternative methods of obtaining follow-up assessments include virtual visit and/or phone visit. The study assessments which may not be feasible to be completed via the alternative methods are listed below:

1. Virtual Visit, i.e. inclusive of video with study subject.

The following assessments may not be (fully) completed with a virtual visit:

- Physical examination (limited review per physician discretion).
- Chest CT or MRI scan to rule out PV stenosis*:
 - Make every effort to schedule in-person imaging as soon as possible.
 - When possible, the subjects could be referred to a local imaging center for assessment.
Local imaging technicians would require study training and delegation prior to assessment.
- NIH Stroke Scale assessment (limited review per physician discretion).

2. Phone Visit, i.e. no video with the subject.

The following assessments may not be (fully) completed with a phone visit:

- Physical examination (limited review per physician discretion).
- Chest CT or MRI scan to rule out PV stenosis*:
 - Make every effort to schedule in-person imaging as soon as possible.
 - When possible, the subjects could be referred to a local imaging center for assessment.
Local imaging technicians would require study training and delegation prior to assessment.
- NIH Stroke Scale assessment.

* Subjects who have experienced symptoms or adverse events suggestive of PV stenosis are required to receive a chest CT or MRI scan to rule out PV stenosis.

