10.11 Subject Lost to Follow-Up

The Investigator will attempt to contact a subject at least three times prior to designating them as lost-to-follow-up subjects; two of these attempts should include attempting to contact subject via registered mail. The Investigator will document the date and type of attempted communication and will complete

the Study Completion Form when a subject is lost to follow-up. When subjects are lost to follow-up the Investigator will make efforts to confirm the vital status of the subject. If allowed per local regulations, a person identified by the subject is informed of the possibility to be contacted by the principal investigator regarding how to reach the subject and the subject's health status and a civil register may be contacted by the principal investigator to inquire about the subject's whereabouts.

11. Risks and Benefits

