6. Determination of Sample Size

For the primary safety endpoint, a sample size of 269 achieves 81% power to detect a difference of at least -4.5% using an Objective Performance Criterion (OPC) of 11.5% and a one-sided target level of significance of 0.025. Reference Section 7.9.1 for relevant statistical hypotheses.

Similarly, for the primary effectiveness endpoint, a sample size of 274 yields 86% power to detect a difference of 9% using an OPC of 40% and a one-sided target level of significance of 0.025. Reference Section 7.9.2 for relevant statistical hypotheses.

Assuming a drop-out rate of 12%, as well as accounting for eligibility/screen failures, the enrollment goal of up to 376 subjects should be sufficient.

7. Statistical Methods

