7.9.2 Primary Effectiveness Objective

Primary Effectiveness Objective

To demonstrate that the primary effectiveness rate associated with the DiamondTemp ablation system is higher than the pre-specified Objective Performance Criterion (OPC).

Hypothesis

Revision 1

Page 11 of 18

 H_0 : $P \leq P_0$

 $H_1: P > P_0$

where $P_0 = 40\%$ (Effectiveness OPC), and higher effectiveness rates are better.

Endpoint Definition and Derivation

The primary effectiveness endpoint is defined as freedom from documented Atrial Fibrillation (AF), Atrial Flutter* (AFL) and Atrial Tachycardia (AT) episodes following the blanking period (3-month followup post-ablation procedure) through the end of the effectiveness evaluation period (12-month followup post-ablation procedure).

An effectiveness failure is defined by any of the following events:

- Inability to electrically isolate all accessible targeted pulmonary veins during the ablation procedure.
- Documented episodes of AF, AFL or AT lasting ≥ 30 seconds in duration as evidenced by electrocardiographic data during the effectiveness evaluation period.
- DC cardioversion for AF, AFL or AT during the effectiveness evaluation period.
- A repeat ablation procedure to treat AF, AFL or AT during the effectiveness evaluation period.
- Use of a new or previously failed anti-arrhythmic drug (AAD) at a dose greater than the highest ineffective dose for AF during the effectiveness evaluation period.
- Use of a non-study device for ablation of any AF targets during the index or repeat ablation procedure during the blanking period.
- More than one (1) repeat ablation procedure during the blanking period.

The blanking period for a subject starts on the date of the index ablation procedure (day 0) and ends on day 90 post index ablation.

The effectiveness evaluation period for a subject starts on day 91 post index ablation and ends on the study exit date or day 410 post index ablation (i.e., close of the 12-month visit window), whichever is earlier.

If a primary effectiveness failure event occurs post day 365 and within the effectiveness evaluation period, the date of the event will be set to day 365 so that these events will be accounted for in the 12month Kaplan-Meier estimate of the primary effectiveness endpoint.

Performance Requirements

The null hypothesis will be rejected if the one-sided 97.5% lower confidence bound of the primary effectiveness rate is greater than 40%.

[figure not shown]

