Rationale for Performance Criteria

The performance goal was derived based on the minimum 12-month success rate for persistent AF recommended in the 2017 HRS Expert Consensus Statement on Catheter and Surgical Ablation of AF.

^{*} Occurrence and/or ablation of cavotricuspid isthmus (CTI)-dependent AFL, as confirmed by entrainment maneuvers during EP testing at any time during this study is not a primary effectiveness failure because it is not considered an iatrogenic arrhythmia following a left atrial ablation procedure for AF.

Revision 1

Page 12 of 18

Analysis Methods

The components of the primary effectiveness composite endpoint will be summarized to show the number and percentage of subjects meeting each component.

The primary effectiveness rate will be analyzed using the Kaplan-Meier method with the log-log transformation to compute the two-sided 95% confidence interval. The null hypothesis will be rejected if the one-sided 97.5% lower confidence bound of the primary effectiveness rate is greater than 40%.

Additionally, a corresponding one-sided p-value may be constructed as follows. First compute the zstatistic using the below formula:

$$z = \frac{\log(-\log(S(t))) - \log(-\log(0.4))}{\sqrt{\sigma(t)^2/(S(t) * \log(S(t)))^2}}$$

Where S(t) is the Kaplan-Meier estimate of the primary effectiveness rate at 12 months (365 days) post index ablation, and $\sigma^2(t)$ is the Greenwood's estimate of the variance of the survivor function S(t) at time t. The one-sided p-value will then be computed from the standard normal distribution as P(Z<z), which is the area of the standard normal distribution less than z since log(-log(S(t))) will be less than log(-log(0.4)) if S(t) > 0.4.

The following subgroup analyses are prospectively defined: geography (US/Canada and Europe), gender (female and male), and age (≤65 and >65 years). The log-rank test will be used to test homogeneity of the primary effectiveness endpoint results between the subgroups.

Determination of Subjects/Data for Analysis

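### SAP 7.4 censors early withdrawals from the rhythm-based primary endpoint at last study contact, so any time after their last rhythm recording counts as arrhythmia-free and can only raise the success rate

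*SAP*

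**What the plan says.** SAP 7.4 describes the main analysis of both primary objectives. Missing data are not imputed, and "subjects who discontinue prematurely will be censored at their last study contact date in the Kaplan-Meier analysis". Neither document defines the last study contact date.

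SAP 7.9.2 sets no separate rule for effectiveness. Its first recurrence criterion is an AF, AFL or AT episode of at least 30 seconds "in duration as evidenced by electrocardiographic data during the effectiveness evaluation period". The evaluation period "starts on day 91 post index ablation and ends on the study exit date or day 410 post index ablation", so it is not tied to the last recording. Success is judged on the "Kaplan-Meier estimate of the primary effectiveness rate at 12 months (365 days) post" index ablation, with a log-log lower 97.5% bound that must exceed 40%.

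Rhythm data come from 12-lead ECGs and 24-hour Holters at 3, 6 and 12 months, two one-minute event-monitor recordings per month after blanking, and recordings prompted by symptoms (Protocol 10.2, Table 8; 13.3).

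The protocol also allows contacts that need not include a recording. In extenuating circumstances, "the alternative methods of obtaining follow-up assessments include virtual visit and/or phone visit" (10.7.7). There are unscheduled visits (10.7.8) and attempts to trace subjects who cannot be reached (10.11).

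**The concern.** The two primary endpoints need different evidence that a subject is still event-free. A conversation can establish that no serious adverse event has occurred. It cannot establish sinus rhythm. A subject who is disengaging may stop using the hand-held monitor and still be reachable. Under SAP 7.4 that subject stays in the risk set until the contact, although a recurrence after the last recording had no means of being recorded.

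The estimate affected is the one that decides the trial. There is no control arm in which a similar error could offset it, so an upward shift goes directly into the comparison with 40%.

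**Working it through.** **1. Design inputs (SAP 6).** N = 274, 49% against 40%, one-sided alpha 0.025, 12% dropout. The stated power is 86%. A one-sample z-test with the null variance in the critical value gives

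Φ[(0.09 − 1.96·√(0.40·0.60/274)) / √(0.49·0.51/274)] = Φ[(0.0900 − 0.0580)/0.0302] = Φ(1.06) = 85.5%,

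which agrees. Allowing for dropout, 274/0.88 = 311.4, so 311 or 312 subjects are simulated.

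**2. Direction.** The Kaplan-Meier estimate is the product of (1 − d/r) over event times, with d events among r at risk. Hold the observed events fixed and move a censoring date later: each r stays the same or grows, each factor stays the same or rises, and so does the product. This needs no assumption about hazard or dropout.

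**3. Hand check of size.** These are assumptions, not figures from the documents: constant hazard from day 91 to day 365 (274 days, by coincidence equal to N), last recording uniform over that span for the 12% who drop out, the same gap for each of them, and no failure ascertained in the gap. At a true 49%:

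- Hazard h = −ln(0.49)/274 = 0.7133/274 = 0.002603 per day.
- Days at risk per subject with no gap: 0.88 × 0.51/0.002603 + 0.12 × (1 − 0.51/0.7133)/0.002603 = 172.4 + 13.1 = 185.5.
- Days added by the gap: 0.12 × mean of e^(−hR)·min(gap, 274 − R), with R uniform on 0 to 274. This is 2.47 days for a 30-day gap and 6.78 days for a 90-day gap.
- Estimate: exp(−0.7133 × 185.5/187.97) = 49.5% for 30 days, and exp(−0.7133 × 185.5/192.28) = 50.2% for 90 days.

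**4. Simulation of the SAP test.** Same assumptions, n = 311, Kaplan-Meier with Greenwood variance and the SAP's log-log z-statistic at day 365. The half-ascertained column assumes that half of the failures in the gap come to light at the contact.

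| Gap (days) | Mean estimate at true 49%, none ascertained | Type I error at true 40%, none ascertained | Type I error at true 40%, half ascertained |
|---|---|---|---|
| 0 | 49.0% | 2.2% | – |
| 30 | 49.5% | 3.9% | 2.6% |
| 60 | 50.0% | 4.6% | 3.3% |
| 90 | 50.4% | 6.5% | 3.4% |
| 180 | 51.3% | 14.4% | 6.0% |

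Monte Carlo error is about 0.3 points for a type I error near 3%. Repeat runs gave 3.1% to 3.9% at 30 days and 6.5% to 7.1% at 90 days with none ascertained, and 2.5% to 3.9% over 30 to 90 days with half ascertained.

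**5. Shape of recurrence.** If 40% of failures fall in the first 14 days after day 91, the type I error with none ascertained is 3.2%, 3.6%, 4.4% and 7.8% for gaps of 30, 60, 90 and 180 days.

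**6. Candidate rules, half of gap failures ascertainable.** Ending follow-up of all early withdrawals at the last recording returns about 49.0% at a true 49%, with a type I error of about 2.2%. Censoring only the event-free at the last recording, while counting later failures, gives 48.6%, 48.5% and 48.2% for gaps of 60, 90 and 180 days. Power then falls to 79% at 180 days, from about 86% with no gap.

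**The case against.** The strongest reply is that the protocol makes a long gap unlikely. Every scheduled visit in the evaluation period includes an ECG and a Holter. Event recordings are due twice a month and are transmitted wirelessly to the core lab (13.3). A subject whose last contact is a clinic visit with its ECG has no gap, and a compliant subject has one of about two weeks. Gaps of 7 and 15 days give type I errors of only 2.4% and 2.9%. Longer gaps require a subject to stop recording and yet remain in contact. This stands, and it makes the bias conditional.

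A reader might infer that a phone visit means recording has stopped. Protocol 10.7.7 does not support that: event-monitor and Holter recording are not among the assessments it says may be incomplete, and Holter data are sent remotely (10.7.4 to 10.7.6). A reader might also take the tracing of lost subjects to move the censoring date. Protocol 10.11 says "When subjects are lost to follow-up the Investigator will make efforts to confirm the vital status of the subject", but nothing there makes a vital-status check a study contact, and 10.9 bars data collection after withdrawal. The undefined term leaves the question open; it does not settle it against the plan.

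A contact can also reveal a cardioversion, a repeat ablation or a drug change, all of which are failures. The figures with none ascertained are therefore upper values for each gap.

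Finally, the tipping-point analysis in SAP 7.4 turns the same dropouts into failures one at a time, so a fragile pass would be visible. But it orders dropouts by the same censoring dates, and the decision stays with the main-analysis bound.

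**Conclusion.** The point holds in conditional form. SAP 7.4 applies to a rhythm endpoint a censoring date that does not require rhythm evidence, and SAP 7.9.2 does not correct it. Any error favours success. Its size depends on a gap that the documents do not give: zero if the last contact carries a recording, and about 0.5 to 1.4 points at a true 49% for gaps of 30 to 90 days in all dropouts. The corresponding type I error at 40% is about 3-7% with none ascertained and about 2.6-3.4% with half ascertained, against about 2.2% with no gap. All of this assumes 12% dropout, dropout unrelated to recurrence, and a constant hazard; early-clustered recurrence gives smaller effects.

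Against the assumed 9-point margin the shift is small, so it matters mainly for a result close to the criterion. Two stronger readings are not supported. The documents do not show that the success rate is inflated, only that the rule permits it. The 14% type I error is a stress case that needs a six-month gap in every dropout. Nor does the contact-date rule extend to the secondary objectives: SAP 7.4 states it for the primary objectives only.

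**What to change.** In SAP 7.4 and 7.9.2, before database lock:

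- **Primary effectiveness, main analysis.** End follow-up of every early withdrawal at the last evaluable rhythm recording (12-lead ECG, Holter or event-monitor transmission). Apply this identically to subjects with and without a later-reported event. Failures up to that date count at their own dates. Define evaluable without regard to the rhythm shown.
- **Conservative sensitivity analysis.** Count failures documented after that date (cardioversion, re-ablation, AAD change) at their own dates. State that this version is biased downward, because it keeps late failures while dropping the matching event-free time.
- **Second sensitivity analysis.** Report the last-contact version.
- **Primary safety.** Keep the last study contact date and define it.
- **Secondary objectives 2, 3, 5 and 6.** The SAP states no censoring date. Use the same recording rule for the rhythm-based ones, noting that for objective 3 AAD use can be ascertained by contact.

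The cost is a few sentences in the SAP and a rerun of the tipping-point analysis on the new dates. No new data are needed, since the core lab already reviews event recordings, Holters and the 3, 6 and 12-month ECGs (Protocol 13.3). The estimate may become slightly less favourable, and a few late failures move from the main analysis to the sensitivity analysis.

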7.5 Adjustments for Multiple Comparisons

No adjustment for multiple comparisons is needed or planned for this study.

The study will be considered successful when both the primary safety objective and the primary effectiveness objective are met. For each primary objective, the sample size ensures a power of at least 80% for a one-sided hypothesis test with alpha level of 0.025.

Diamond-AF II Statistical Analysis Plan Form Medtronic Revision 1 Page 8 of 18

The secondary and ancillary study objectives will be analyzed descriptively without hypothesis testing, therefore adjustment for multiple comparisons is not applicable.

7.6 Demographic and Other Baseline Characteristics

Demographic and baseline characteristics will be summarized for the mITT Set. Demographic variables include age, sex, and geographic ancestry. Baseline characteristics include height, weight, BMI, and duration of disease.

Medical and Surgical History will be summarized for the mITT Set. Any past medical findings or surgical procedures will be summarized by Body System.

The pre-treatment physical exam will be summarized for the mITT Set. Any findings will be summarized by Body System.

7.7 Treatment Characteristics

Procedural characteristics of the DiamondTemp ablation treatment will be summarized as an ancillary objective.

All medications taken from the screening date up to the index procedure and after the index procedure through the last study visit will be summarized based on the World Health Organization (WHO) Drug dictionary.

7.8 Interim Analyses

No formal statistical interim analyses are planned for this study.

7.9 Evaluation of Objectives

All study objectives will be analyzed using the mITT population. Additionally, sensitivity analyses of the primary safety and effectiveness objectives will be performed using the ITT and PP populations.

The DIAMOND-AF II study will be considered successful when both the primary safety objective and the primary effectiveness objective are met.

